**Table 4. Summary of Study Assessments**

Assessments	Baseline (In person)	Day 4+/-2 (by phone)	Day 7+/-2 (In person/by phone)	Day 14+/-2 (In person/by phone)
Demographics and Cancer Diagnosis 	X			
Medication History 	X			
Karnofsky Performance Status 	X			
Dyspnea Survey 	X			
O2 saturation and Respiratory Rate	X			
Cancer Dyspnea Scale 	X	X	X	X
Edmonton Symptom Assessment Scale 	X	X	X	X
Dyspnea Numeric Rating Scale 		Daily	Assessment	
Dyspnea Borg scale 	X	X	X	X
Spirometry Measures 	X	X	X	X
EORTC QLQ-C30 	X	X	X	X
Adverse effects 		X	X	X
Global assessment 		X	X	X
Pill count			X	X
Check of blinding			X	

 patient initials, medical record number, date of birth, sex, race, education, marital status, cancer diagnosis, co-morbidities, cause(s) of dyspnea.

 medications that could be used to treat dyspnea, including scheduled and as needed opioids, bronchodilators, and steroids will be documented.

 an 11-point assessment scale that rates patients' functional status between 0% (death) and 100% (completely asymptomatic) based on their ambulation, activity level, and disease severity (Schag et al. 1984).

 characterization of patients dyspnea including the following: presence of dyspnea at rest, average dyspnea in last 24 hours, worse dyspnea in last 24 hours, best dyspnea in last 24 hours, number of episodes of exacerbation per day, triggers of breakthrough dyspnea, average duration of each episode, current treatment for breakthrough dyspnea. It also adopted 3 questions from EORTC Lung module about dyspnea.

 validated 12-item questionnaire specifically designed to assess the quality of dyspnea in cancer patients during the past few days (Tanaka et al. 2000). Each item has a score between 1 and 5, for a maximum of 60. There are sub-scores for sense of effort, anxiety, and discomfort.

 validated questionnaire that measures 10 common symptoms in the past 4 hours (pain, fatigue, nausea, depression, anxiety, drowsiness, shortness of breath, appetite, sleep, and feeling of well being) using numeric rating scales (Bruera et al. 1991).

 a 0 (no dyspnea) to 10 (worst dyspnea) categorical scale validated for rating the severity of dyspnea (Dorman et al. 2007, Gift and Narsavage 1998, Powers and Bennett 1999).

 a 0 to 10 categorical scale for rating the severity of dyspnea. It is a ratio scale with descriptive anchors throughout the range in which a rating of 8 signifies breathlessness twice as severe as 4, which in turn is twice as severe as 2 (Dorman et al. 2007, Gift and Narsavage 1998, Kendrick et al. 2000, Powers and Bennett 1999).

 the MicroLoop Spirometer (Micro Direct Inc, Lewiston, ME) will be used at baseline, day 7 and day 14. It is approved by the American Thoracic Society and US Food and Drug Administration. Various spirometry parameters will be obtained, such as vital capacity (VC), forced expiratory volume in 1 second (FEV1), forced vital capacity

(FVC), FEV1/FVC, peak inspiratory flow, and peak expiratory flow. As an exploratory measure, patients will also be asked to use the portable Microlife PF 100 Peak Flow Meter (Microlife, Clearwater, FL) to measure peak flow and FEV1 on a daily basis.

10 a well-validated quality of life instrument for cancer patients, consisting of 30 items that encompasses 3 symptom scales (pain, fatigue, nausea/vomiting), 6 single-item symptom items, 5 functional scales (physical, cognitive, role, emotional, and social), and one scale assessing global health status/quality of life. Each scale consists of 2-5 items. All items have four response categories (not at all, a little, quite a bit, very much), except for 2 items assessing overall health status/quality of life, which use a seven-point scale.

11 adverse effects related to the use of dexamethasone, such as edema, fever, infections, insomnia, anxiety, personality change, dyspepsia will be rated using the National Cancer Institute Common Terminology Criteria for Adverse Events version 4.03.

12 patients will be asked about their dyspnea (worse, about the same, or better) comparing the level of dyspnea before and after the study (Guyatt *et al.* 1993, Redelmeier *et al.* 1996).

13 patients will be asked to record their study medication use, as well as any use of opioids and bronchodilators for relief of dyspnea.

**C.11. Patient Safety, Monitoring, and Confidentiality.** Prior to study initiation, all research staff participating in this study will receive an orientation to the devices and forms in this study to ensure consistent assessments. During the study, trained research staff will be performing study assessments and monitoring the patient carefully throughout the study period. In addition to daily phone calls, patients will be given the contact information of the research nurse in case they develop any significant adverse effects, and will be treated as they arise as per clinical practice. The study may be discontinued at the discretion of the treating physician or study principal investigator. Regulatory monitoring will be provided by the principal investigator, the Institutional Review Board, and the Data Safety and Monitoring Board. Patient confidentiality will be ensured by use of patient initials, secure storage of clinical data, and anonymous reporting.

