**1.0 Objectives**

**A. Objectives**

**A.1. Primary Objective.** To determine the feasibility of conducting a randomized controlled trial (blinded phase) on dexamethasone in cancer patients with dyspnea. Our working hypothesis is that at least 50% of patients will complete the dyspnea numeric rating scale (NRS) on day 7+/-2.

**A.2. Objective #2.** To compare the intensity of dyspnea (NRS), forced expiratory volume (FEV1) and quality of life in cancer patients between baseline and after 4 days of dexamethasone use. Our *working hypothesis* is that 4 days of dexamethasone will improve dyspnea, respiratory function and quality of life for cancer patients.

**A.3. Objective #3.** To compare the intensity of dyspnea (NRS, cancer dyspnea scale), FEV1, and quality of life in cancer patients between baseline and after 7 days of dexamethasone use. Our *working hypothesis* is that 7 days of dexamethasone will improve dyspnea, respiratory function and quality of life for cancer patients.

**A.4. Objective #4.** To compare the intensity of dyspnea (NRS, cancer dyspnea scale), FEV1, in cancer patients between the dexamethasone arm and the placebo arm at 4 and 7 days. Our *working hypothesis* is that dexamethasone will improve dyspnea, and respiratory function for cancer patients compared to placebo.

**A.5. Objective #5.** To compare the intensity of dyspnea (NRS, cancer dyspnea scale), FEV1, and quality of life in cancer patients after 7 days of dexamethasone between the dexamethasone arm (8mg BID for 4 days followed by 4mg BID for 3 days) and the placebo arm (4mg BID for 7 days during the open label phase). Our *working hypothesis* is that a higher dose of dexamethasone will improve dyspnea, respiratory function and quality of life for cancer patients compared the lower dose.

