**C.3. Study screening.** A 2 step consent process will be used. A verbal script is provided in the Appendix P. First, a verbal consent will be obtained by the study staff to proceed with screening of potential participants for eligibility and to characterize their dyspnea using the dyspnea survey and the cancer dyspnea scale. Eligible patients will then be formally enrolled onto the study after they have signed the informed consent indicating a willingness to participate in the trial. The number of patients screened, approached, eligible and enrolled will be documented. Reasons for refusal for eligible patients will also be captured.

**C.4. Randomization.** A computer generated sequence in permuted blocks will be used to assign patients to either dexamethasone or placebo via CORE, a secured website. We will stratify by FEV1/FVC ratio (<0.8 vs.  $\geq 0.8$ ). CORE will set up a Randomization website and Investigational Pharmacy personnel will perform the randomization assignment. [name], our research manager, will provide the necessary CORE training for the research team.

**C.5. Blinding.** Both patients and the research staff conducting the assessment will be blinded to the treatment assignment. Placebo capsules identical to dexamethasone 4mg capsules in appearance and taste will be compounded by Green Park Compounding Pharmacy, and both will be dispensed by Investigational Pharmacy at MD Anderson. At the end of the blinded phase, we will assess blinding by asking patients which study arm they believe they have been randomized to.

**C.6. Research staff.** An orientation will be held with research staff involved in this study to introduce them with the study design, and standardize the provision of each intervention.

**C.7. Study Interventions.** The intervention arm will receive dexamethasone 8 mg (2 capsules of 4 mg) given orally twice a day for 4 days, then 4 mg given orally twice a day for 3 days. This dose was chosen partly based on our feasibility data demonstrating that dexamethasone improved dyspnea.

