Dexamethasone is commonly used in oncology practice for management of cerebral edema, spinal cord compression, chemotherapy induced nausea and vomiting, bowel obstruction, pain, anorexia, dyspnea and fatigue. For patients with chronic obstructive pulmonary diseases, systemic corticosteroids have been clearly shown to reduce respiratory symptoms, improve FEV1 and shorten hospitalization in acute exacerbations (Falk et al. 2008, Walters et al. 2009, Wood-Baker et al. 2007). Furthermore, inhaled steroids have been demonstrated to improve various clinical outcomes in COPD patients including the number of physician visits and airway hyperreactivity (Calverley et al. 2007, Lung Health Study Research 2000, Yang et al. 2007). However, the efficacy of corticosteroids for dyspnea has not been clearly elucidated in cancer patients.

Our study proposes to use oral dexamethasone for the management of dyspnea. The dose of dexamethasone we plan to use is 8mg PO BID for 4 days, then 4 mg PO BID x10 more days. This is similar to doses we use for CINV prophylaxis (8-20mg IV/PO prior to chemotherapy, then 4-8mg q12h for up to 4 days after chemotherapy) (Mullin and Beckwith, [www.ifvrh.com/policies\\_quick\\_ref/Treatment\\_of\\_CINV.html](http://www.ifvrh.com/policies_quick_ref/Treatment_of_CINV.html)). This study is purely exploratory in nature, and we do not plan to seek FDA approval for the new indication of dyspnea.

The control arm will receive placebo capsules prepared by a compounding pharmacy (Green Park Compounding Pharmacy) identical in appearance to dexamethasone 4 mg capsules, and will be instructed to take two capsules twice a day for 4 days, followed by one capsule twice a day for 3 days.

In the open label phase, patients assigned to either arm will be asked to take dexamethasone 4 mg orally twice a day for 7 days. Both dexamethasone and placebo capsules used throughout this study will be compounded by Green Park Compounding Pharmacy and dispensed by Investigational Pharmacy at MD Anderson. Dexamethasone/placebo capsules will be provided free of charge to patients during the 14 day study period.

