**C.8. Medication use during study.** We will ask patients to record the use of study medications using a medication diary. We will also keep track of their adherence by asking them to bring their medication boxes for a pill count. Phone call reminders will be provided daily. To document the co-intervention effect on dyspnea, patient use of regular and breakthrough opioids (for any reason) and bronchodilators at enrollment and during the study. Patients will receive daily phone calls for reminders and assessments. They can take it as soon as possible if they forget a dose.

**C.9. Feasibility endpoints.** Our primary objective is to test the feasibility of a protocol that uses dexamethasone and placebo for dyspnea, and to determine the feasibility of these two interventions for advanced cancer patients with persistent dyspnea. We will document the following:

- Rates of recruitment and retention (see section D1).
- Reasons for refusal and dropout
- Outcome measure—we will compare the sensitivity of Numeric rating scale and Borg scale to change, and identify key measure for future study
- Participant satisfaction—participants will provide an opinion regarding their satisfaction with study overall

**C.10. Study assessments.** See Table 4 for a detailed description of all study assessments.

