### D.2. Data Analysis

**Primary Objective:** Our primary objective is to determine the completion rate for patients enrolling in this study. Patients who complete the dyspnea NRS on day 72 will be counted as successes. Dropouts are defined as subjects who do not complete the dyspnea NRS on day 7 +/- 2, and will be counted as failures toward the feasibility outcome. We will declare the study as feasible if we observe at least 20 successes, based on a recent review of Supportive Oncology studies in our department in which we found that approximately 50% patients completed their interventional clinical trial.

**Objective #2.** We will test our hypothesis that 4 days of dexamethasone will improve dyspnea, respiratory function and quality of life for cancer patients using paired t-tests.

**Objective #3.** We will test our hypothesis that 7 days of dexamethasone will improve dyspnea, respiratory function and quality of life for cancer patients using paired t-tests. A sample size of 20 per arm will allow us to detect an effect size of 0.9 in the change of dyspnea NRS between baseline and day 7 with an 80% power and an alpha of 5%, assuming a standard deviation of 2.

**Objective #4.** We will test our hypothesis that dexamethasone will improve dyspnea, respiratory function and quality of life for cancer patients compared to placebo using two-sample t-tests on the differences between baseline and 4 and 7 days for each outcome measure.

**Objective #5.** We will test our hypothesis that increased dose results in better outcomes by comparing the first 7 days of treatment arm to the last seven days of the placebo arm. We will use two-sample t-tests on the differences between baseline (day 0 for treatment arm, day 7 for placebo arm) and 7 days later (day 7 for treatment arm, day 14 for placebo arm).

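### The Day 4 window (days 2–6) spans the dose step-down and shares days 5–6 with the Day 7 window, so Day 4 questionnaires have no fixed exposure

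*Combined protocol and SAP*

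**What the plan says.** **Assessment days.** Table 4 (C.10) heads its first two follow-up columns "Day 4+/-2 (by phone" and "Day 7+/-2 (In person/by phone". The Cancer Dyspnea Scale, ESAS, Borg scale and EORTC QLQ-C30 are collected only at baseline and at these windowed contacts and Day 14. The dyspnea NRS is marked as daily. Footnote 9 adds a daily FEV1 from a portable meter as an exploratory measure. It places the clinic spirometer at baseline, day 7 and day 14, although Table 4 also marks spirometry at Day 4.

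**Dosing.** In C.7 the active arm takes its first-step dose "given orally twice a day for 4 days, then 4 mg given orally twice a day for 3 days". The placebo arm follows the same pattern: "two capsules twice a day for 4 days, followed by one capsule twice a day for 3 days".

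**Objectives and tests.** Objective #2 compares outcomes "between baseline and after 4 days of dexamethasone use", and D.2 tests whether "4 days of dexamethasone will improve dyspnea, respiratory function and quality of life for cancer patients using paired t-tests". For Objective #4, D.2 specifies "two-sample t-tests on the differences between baseline and 4 and 7 days for each outcome measure". D.2 does not say which value inside a window is analysed, or what happens to a reading on day 5 or 6.

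**Contacts.** C.8 states: "Patients will receive daily phone calls for reminders and assessments".

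**The concern.** Two objectives attach a conclusion to four days of treatment, and the dose changes at just that point. A window of two days either side lets the Day 4 questionnaires fall on either side of the change. It also lets them fall on days that belong equally to the Day 7 contact, so a single reading could be assigned to either visit.

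C.1 gives the main goal as estimating effect sizes to plan a larger trial. An effect size whose exposure ranges from two dosing days to seven is harder to carry into that plan than one taken at a stated point. The width also has little visible purpose: the Day 4 contact is by telephone, and patients are telephoned every day in any case.

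**Working it through.** This is a count of days. The plan gives no figure of its own to reproduce.

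**Inputs.** Windows: Table 4. Step lengths of 4 days and then 3 days: C.7. Baseline is called day 0 in D.2 (Objective #5), but no section states the calendar day of the first dose, so both conventions are shown.

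**Windows.**
- Day 4: 4 − 2 = 2 to 4 + 2 = 6, giving {2, 3, 4, 5, 6}.
- Day 7: 7 − 2 = 5 to 7 + 2 = 9, giving {5, 6, 7, 8, 9}.
- Shared days: {5, 6}, two of the five days in each window.

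**Dose steps.** If the first dose is on day f, the first step covers days f to f + 3 and the lower step covers days f + 4 to f + 6.
- f = 1: first step on days 1–4, lower step on days 5–7.
- f = 0: first step on days 0–3, lower step on days 4–6.

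**Exposure by the end of the assessment day** (first-step days + lower-step days, assuming full dosing on each day):

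| Day of contact | First dose on day 1 | First dose on day 0 |
|---|---|---|
| 2 | 2 + 0 | 3 + 0 |
| 3 | 3 + 0 | 4 + 0 |
| 4 | 4 + 0 | 4 + 1 |
| 5 | 4 + 1 | 4 + 2 |
| 6 | 4 + 2 | 4 + 3 |

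The lower step has begun on two of the five window days if f = 1 (days 5 and 6), and on three of five if f = 0 (days 4, 5 and 6). Fewer than four days of drug have been taken on two days if f = 1 (days 2 and 3), and on one day if f = 0 (day 2). In each column one day of five gives 4 + 0. It is day 4 if f = 1 and day 3 if f = 0, so the nominal day 4 is itself the right target only under the first convention.

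The counts are taken at the end of the day. A call made before that day's doses sees the exposure of the row above, so the hour of the call matters as well as the date.

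**Which outcomes lack a daily value.**
- Objective #2 (A.2: NRS, FEV1, quality of life): quality of life (QLQ-C30) has none. The NRS is daily. FEV1 is daily if the portable meter is used.
- Objective #4 (A.4: NRS, Cancer Dyspnea Scale, FEV1): the Cancer Dyspnea Scale has none. D.2 also names quality of life here, so QLQ-C30 is affected again.
- Borg and ESAS are windowed too. They are not named in the objectives, but C.9 compares the Borg with the NRS for sensitivity to change, and nothing requires the two to be read on the same day.

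**The case against.** The strongest reply is that little depends on this. The study is an exploratory pilot with a convenience sample, and its primary endpoint is completion of the NRS at day 7 +/- 2, which the Day 4 window does not touch. Of the three outcomes in Objective #2, the NRS is collected daily and FEV1 can be. All of that stands, and it confines the point to the questionnaires and to a missing sentence in D.2 on which NRS value is used.

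The reply can add that a fixed day has a price. Patients may have a Karnofsky status as low as 40%, and D.2 expects only about half to complete. Daily calls do not show that four instruments, including a 30-item one, can be finished on a given day. That also stands, and it is why off-target questionnaires should be kept and not discarded.

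A reader might infer more than the documents support:

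- *That Day 4 is defined as a first-step-dose endpoint.* It is not. Objective #2 speaks only of four days of use, and a day-5 reading does follow four days. The link to the first step is inferred from the schedule. The overlap and the readings before four days do not need that inference.
- *That a day-5 or day-6 reading measures only the lower step.* This depends on recall. The Cancer Dyspnea Scale covers the preceding few days and would span both steps, whereas ESAS covers four hours.
- *That a planned comparison of Day 4 with Day 7 is lost.* D.2 contains none; its Day 4 and Day 7 tests are changes from baseline.
- *That early and late readings are known to differ greatly.* In the physician survey cited in B.4, 37% + 38% = 75% perceived an effect within two days. In the B.5 preliminary data the gap between arm medians is −2 − (−1) = −1 at day 4 and −1 − 0 = −1 at day 8. Patient numbers differ by day there, so neither source settles the matter.
- *That Objective #4 is biased.* The window is the same in both arms, the capsule counts step down in parallel, and assessors are blinded. Noise is the expected result.

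**Conclusion.** The point holds for the Day 4 questionnaires. Under either first-dose convention the window crosses the step-down and shares days 5–6 with the Day 7 window. A compliant Day 4 value of QLQ-C30, the Cancer Dyspnea Scale, Borg or ESAS can reflect fewer than four days of drug, or four days plus one to three at the lower step. The consequence is noise and an unclear exposure definition in secondary objectives.

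The number of patients affected cannot be derived. The plan gives no distribution of contact days, so it could be anywhere from none to all 20 in the dexamethasone arm; placebo patients have no change in drug exposure. The exposure counts assume full dosing on each day and no missed doses. The feasibility decision is unaffected, and so is the NRS provided the exact-day value is analysed. This is a low-cost improvement and not a threat to the trial.

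**What to change.** The change concerns assessment timing only; dosing stays as written.

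1. State in C.7 or C.10 which study day is the first dosing day.
2. In Table 4, target the Day 4 questionnaires to the existing daily call at the end of the fourth dosing day, before the first step-down dose.
3. In D.2, name the NRS from that same day (and the portable-meter FEV1, if it is used) as the Day 4 value for Objectives #2 and #4.
4. Make the Day 4 and Day 7 windows non-overlapping, and state that no reading can serve both. Narrowing the Day 4 side achieves this: the fourth dosing day is day 3 or day 4, outside days 5–9, so the feasibility definition stays as it is.
5. Record the actual day of every questionnaire, and keep those taken off the target day for a sensitivity analysis.

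The cost is a few lines in Table 4, C.7 and D.2, with no added contacts. The downside is that a few Day 4 questionnaires may be missing from the main analysis; the documents give no basis for estimating how many.

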Few clinical studies have addressed the role of corticosteroids for dyspnea in cancer patients. In a case series, Elsayem *et al.* reported significant improvement in dyspnea after administration of high dose steroids among patients with upper airway obstruction (Elsayem and Bruera 2007). In a prospective series, Hardy *et al.* found that 5/13 advanced cancer patients experienced some improvement with dexamethasone, 6/13 had no change and 2/13 did worse (Hardy *et al.* 2001). Matso *et al.* surveyed 120 Japanese palliative care physicians about their use of steroids. 37% of physicians perceived the positive effect of steroids on dyspnea to take place within 24 hours, 38% within 1-2 days, and 24% within 3-7 days (Matsuo *et al.* 2011). The main perceived predictors of steroid efficacy were lymphangitic carcinomatosis, airway obstruction, multiple lung metastases. The main side effects after 1 week of use were hyperglycemia, insomnia, delirium and oral candidiasis. A recent systematic review on dyspnea interventions found no study on corticosteroids, and concluded that high quality randomized controlled trials are needed to examine the effectiveness of corticosteroids for dyspnea (Viola *et al.* 2008). A study examined the effect of prednisone in healthy men on induced dyspnea using inspiratory resistors and breathholding, and concluded that prednisone intake was associated with significant increase in minute ventilation during breathing compared to placebo (Kallas De Carvalho *et al.* 2002).

[figure not shown]

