### 3.0 Experimental Approach

**C.1. Overall Study design.** This is a 2-arm, double blind, parallel randomized controlled trial of dexamethasone and placebo for cancer patients with dyspnea (Figure 1). The main goal of this study is to determine the effect size for both dexamethasone and placebo arm to inform a larger, adequately powered confirmatory randomized controlled trial. For this preliminary study, we plan to enroll 20 patients per arm, with a total of 40 patients for the entire study (see statistical considerations for more details). Patients will be randomized to either dexamethasone or placebo for 7 days in a blinded fashion; this will be followed by an open label phase in which patients in both arms would take dexamethasone for 7 days. The rationale for the open label phase is to give all patients an opportunity to try the study medication, and to examine the use of dexamethasone at a different dose as an exploratory endpoint (objective #5). Based on our experience conducting symptom control trials, we believe this study design is feasible and would not add undue burden for patients. To reimburse patients for their time and effort, we will provide a gift card for \$20 per visit (day 7+/-2 and day 14+/-2).

**C.2. Eligibility Criteria.** The eligibility criteria are shown in Table 2.

Table 2. Study Eligibility Criteria

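### On the planned dosing calendar, the day 14 ±2 window lets the placebo arm's Objective #5 end value be read 1 to 2 days after its last dexamethasone dose, which could favour the higher-dose hypothesis by an unknown amount

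*Combined protocol and SAP*

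**What the plan says.** Section C.1 sets out two consecutive phases. The blinded one comes first: "Patients will be randomized to either dexamethasone or placebo for 7 days in a blinded fashion". In the second, both arms receive open-label dexamethasone for a further week. Section C.7 gives the detail of that second phase: "patients assigned to either arm will be asked to take dexamethasone 4 mg orally twice a day for 7 days". The same section describes the active schedule as "8mg PO BID for 4 days, then 4 mg PO BID x10 more days", and says capsules are supplied "free of charge to patients during the 14 day study period".

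Table 4 heads its last column "Day 14+/-2 (In person/by phone" and gives the preceding visit the same tolerance around day 7. Section D.2 defines Objective #5 by nominal days: baseline is day 0 in the dexamethasone arm and day 7 in the placebo arm, and the end value is "7 days later (day 7 for treatment arm, day 14 for placebo arm". It states no window rule and does not tie either reading to a dose date.

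The Objective #5 outcomes (A.5) are the dyspnea NRS, the cancer dyspnea scale, FEV1 and quality of life. Table 4 makes the NRS a daily assessment, and its spirometry footnote adds a daily portable FEV1 as an exploratory measure. MicroLoop spirometry, the QLQ-C30 and the cancer dyspnea scale are collected only at the scheduled assessments.

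**The concern.** The two groups in Objective #5 reach their end value at different points of the dosing calendar. For the dexamethasone arm, day 7 is followed by more dexamethasone, so a late visit still falls within treatment. For the placebo arm, day 14 is the end of all study drug, so a late visit falls after treatment. If benefit fades once dexamethasone stops, lateness weakens only the lower-dose group's result. That is the direction of the hypothesis in A.5, so part of an apparent dose effect could come from scheduling.

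The placebo arm's baseline has a related weakness. It is read in the day 7 ±2 window, so on day 8 or 9 the patient may already have begun open-label drug. A baseline already improved by drug shrinks that arm's measured change, again in favour of the higher dose.

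**Working it through.** **Inputs.** Blinded phase 7 days and open-label phase 7 days (C.1); active schedule 4 + 10 = 14 days (C.7); visit windows days 5–9 and 12–16 (Table 4); 20 per arm (D.1); SD 2, effect size 0.9, 80% power, alpha 5% (D.2, Objective #3). The documents do not give the open-label start rule, the spread of visits within the window, or the rate at which effect is lost after the last dose.

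**The plan's own figure.** Objective #5 has no power statement. The only one is under Objective #3. Read as a two-sided, two-sample comparison of a standardised effect, it reproduces: Φ(0.9 × √(20/2) − 1.96) = Φ(0.886) = 81.2%, or 79.2% by the noncentral t. It does not reproduce for the paired test named there (96.8%), but that is a separate matter. As a yardstick, 0.9 × SD 2 = 1.8 NRS points.

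**Step 1: calendar with no gap, first dose on day 1.** The last blinded day is 7 and the last open-label day is 14. Days past the last dose = max(0, visit day − 14).

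| Placebo-arm visit day | 12 | 13 | 14 | 15 | 16 |
|---|---|---|---|---|---|
| Days of dexamethasone taken | 5 | 6 | 7 | 7 | 7 |
| Days past last dose | 0 | 0 | 0 | 1 | 2 |

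| Dexamethasone-arm visit day | 5 | 6 | 7 | 8 | 9 |
|---|---|---|---|---|---|
| Days of dexamethasone taken | 5 | 6 | 7 | 8 | 9 |
| Days past last dose | 0 | 0 | 0 | 0 | 0 |

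Early visits give equal exposure in the two arms; the late ones do not. If the first dose is on day 0, the last is on day 13 and the placebo-arm gaps become 0, 0, 1, 2 and 3 days.

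**Step 2: open-label drug starting no earlier than the day 7 visit.** A dexamethasone-arm patient seen on day 8 or 9 is then 1 or 2 days past the last blinded dose. A placebo-arm patient seen on day 9 takes drug on days 9 to 15, so the gap on day 16 is 1 day. For such patients the asymmetry shrinks or reverses.

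**Step 3: placebo-arm interval.** Baseline on days 5–9 and end value on days 12–16 give an interval of 12 − 9 = 3 to 16 − 5 = 11 days, against a nominal 7.

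**Step 4: possible size, for an NRS read at the visit.** Bias = (share of placebo arm read on days 15–16) × (share of effect lost) × (low-dose effect). All three are assumptions: share read late 0.2 to 0.4 (0.4 is two of five days, visits evenly spread), loss 25% to 100%, effect 1 to 2 points. With SE = 2 × √(2/20) = 0.632 and 38 degrees of freedom, the two-sided rejection rate when the doses truly do not differ is:

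| Share late × loss × effect | Bias (points) | Bias/SE | Rejection rate |
|---|---|---|---|
| 0.2 × 0.25 × 1 | 0.05 | 0.08 | 5.1% |
| 0.4 × 0.50 × 1 | 0.20 | 0.32 | 6.1% |
| 0.4 × 0.50 × 2 | 0.40 | 0.63 | 9.5% |
| 0.4 × 1.00 × 2 | 0.80 | 1.26 | 23.4% |

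These cover late end values only. They exclude the baseline problem and assume the Step 1 calendar.

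**The case against.** The strongest reply is that the dexamethasone arm is not guaranteed to be on drug at its day 7 visit. The active schedule in C.7 implies 14 unbroken days, but it describes a dose and is not a dispensing rule. C.5 checks blinding when the blinded phase ends, and Table 4 puts that check and a pill count at the day 7 ±2 visit, so the switch may happen there. This stands: a reader might infer that the comparator is always read on drug and that the error is one-sided, but the documents support this only for the gap-free calendar.

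Second, D.2 names day 14 itself and the NRS is collected daily, so an NRS for that day should exist whatever the visit date. This largely stands. The NRS is exposed only if the visit value is used, and D.2 does not exclude that: the feasibility endpoint counts an NRS at day 7 ±2 despite daily collection. The cancer dyspnea scale asks about the last few days, which dilutes a gap of 1 or 2 days. MicroLoop FEV1 and the QLQ-C30 remain exposed.

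Third, no size can be taken from the documents. The physician survey cited in B.4, with 37% perceiving benefit within 24 hours and "38% within 1-2 days", concerns onset. A reader might infer that benefit is lost equally fast, but the survey says nothing about stopping.

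Fourth, a ±2 day window is reasonable for symptomatic outpatients when about 50% completion is expected, and C.1 calls this objective exploratory. Both points stand, and both bear on the remedy and the priority.

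**Conclusion.** The point holds on the planned calendar. Placebo-arm readings on days 15–16 fall 1 to 2 days after the last open-label dose, while dexamethasone-arm readings on days 5–9 fall within dosing. Any loss of effect after stopping would then favour the higher-dose hypothesis, and a placebo-arm baseline read on days 8–9 could add to this. It rests on a gap-free open-label start and on some loss of effect within two days; the documents secure neither.

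The size is unknown. The 0.05 to 0.8 point range is a set of assumptions to be read against about 1.8 points detectable, and it should not be quoted as an estimate. MicroLoop FEV1 and the QLQ-C30 are the most exposed outcomes, the cancer dyspnea scale less so, and the NRS only if its visit value is used.

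A reader might also infer that day-14 adverse-effect and quality-of-life readings are biased because both arms may be off drug. The documents do not support that as a between-arm bias: the gap is common to both arms, D.2 plans no day-14 adverse-effect comparison, and day-14 quality of life enters only through the placebo arm of Objective #5. This is a minor point about an exploratory objective, worth correcting because correction is nearly free.

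**What to change.** In D.2, Objective #5:

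- In both arms, take the NRS values from the daily NRS. Baseline is the last reading before the first dexamethasone dose, and the end value is the reading on the seventh dexamethasone dosing day. Identify both days from the medication diary (C.8).
- Use the daily portable FEV1 in the same way, as a supporting analysis, since it is labelled exploratory.
- Keep the ±2 day visit windows and all visit data. Flag visit-only readings taken after the last dose, and placebo-arm baselines taken after the first open-label dose. Report a sensitivity analysis without the flagged values.

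Separately, reconcile C.1, C.5, C.7 and Table 4 so that the open-label start relative to the day 7 visit is clear. Which rule applies is for the investigators to state.

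Narrowing the last window to day 14 −2/+0 is a less good remedy. With evenly spread visits the placebo arm would average (5 + 6 + 7)/3 = 6 days of drug, against (5 + 6 + 7 + 8 + 9)/5 = 7 in the dexamethasone arm under gap-free dosing, which again favours the higher dose. Dropping late visits outright would also lose visit-only data with 20 per arm.

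The cost is a little more analysis work and fewer visit-only values in the sensitivity analysis. No new data collection is needed.
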